Attachment 4. Protocol JP04 Addendum Hepatic Monitoring Tests for Treatment-Emergent Abnormality

See Section 3.9.3.1.1 for guidance on appropriate test selection.

The Lilly-designated central laboratory must complete the analysis of all selected testing except for microbiology testing.

Local testing may be performed *in addition to central testing* when necessary for immediate participant management.

Results will be reported if a validated test or calculation is available.

Hematology	Clinical Chemistry
Hemoglobin	Total bilirubin
Hematocrit	Direct bilirubin
Erythrocytes (RBCs - red blood cells)	Alkaline phosphatase (ALP)
Leukocytes (WBCs - white blood cells)	Alanine aminotransferase (ALT)
Differential:	Aspartate aminotransferase (AST)
Neutrophils, segmented	Gamma-glutamyl transferase (GGT)
Lymphocytes	Creatine kinase (CK)
Monocytes	Other Chemistry
Basophils	Acetaminophen
Eosinophils	Acetaminophen protein adducts
Platelets	Alkaline phosphatase isoenzymes
Cell morphology (RBC and WBC)	Ceruloplasmin
Coagulation	Copper
	Ethyl alcohol (EtOH)
Prothrombin time, INR (PT-INR)	Haptoglobin
Serology	Immunoglobulin IgA (quantitative)
Hepatitis A virus (HAV) testing:	Immunoglobulin IgG (quantitative)
HAV total antibody	Immunoglobulin IgM (quantitative)
HAV IgM antibody	Phosphatidylethanol (PEth)
Hepatitis B virus (HBV) testing:	Urine Chemistry
Hepatitis B surface antigen (HBsAg)	Drug screen
Hepatitis B surface antibody (anti-HBs)	Ethyl glucuronide (EtG)
Hepatitis B core total antibody (anti-HBc)	Other Serology

Hepatitis B core IgM antibody	Anti-nuclear antibody (ANA)
Hepatitis B core IgG antibody	Anti-smooth muscle antibody (ASMA) ^a
HBV DNA ^b	Anti-actin antibody ^c
Hepatitis C virus (HCV) testing:	Epstein-Barr virus (EBV) testing:
HCV antibody	EBV antibody
HCV RNA ^b	EBV DNA ^b
Hepatitis D virus (HDV) testing:	Cytomegalovirus (CMV) testing:
HDV antibody	CMV antibody
Hepatitis E virus (HEV) testing:	CMV DNA ^b
HEV IgG antibody	Herpes simplex virus (HSV) testing:
HEV IgM antibody	HSV (Type 1 and 2) antibody
HEV RNA ^b	HSV (Type 1 and 2) DNA ^b
Microbiology ^d	Liver kidney microsomal type 1 (LKM-1) antibody
Culture:	
Blood	
Urine	

^a Not required if anti-actin antibody is tested.

^b Reflex/confirmation dependent on regulatory requirements, testing availability, or both.

^c Not required if anti-smooth muscle antibody (ASMA) is tested.

^d Assayed ONLY by investigator-designated local laboratory; no central testing available.

Attachment 5. Protocol JP04 Addendum Restricted and Prohibited Concomitant Therapy

This attachment describes medications, treatments, and drug classes restricted or prohibited, with exceptions and conditions for use during the study treatment period (there are no prohibited therapies during the follow-up period). Participants who, in the assessment by the investigator, require the use of any of the prohibited treatments for clinical management should be removed from the trial. Participants may receive other supportive therapy or vaccinations that the investigator deems to be medically necessary.

Vaccine Guidance

Live vaccines are not permitted while on treatment and for at least 3 months after the last dose of abemaciclib.

Guidance for Modulators of CYP3A

Abemaciclib is extensively metabolized through oxidation by CYP3A. In clinical drug interaction studies,

- coadministration of clarithromycin, a strong CYP3A inhibitor, increased exposure (AUC) of abemaciclib by 3.4-fold (Study I3Y-MC-JPBE), and
- coadministration of rifampin, a strong CYP3A inducer, decreased exposure of abemaciclib by 95% (Study I3Y-MC-JPBF).

Strong inhibitors of CYP3A (given via non-topical routes of administration) should be substituted or avoided if possible (see list below). This includes grapefruit or grapefruit juice. In particular, avoid oral administration of the very strong CYP3A inhibitor, ketoconazole.

If coadministration with a strong CYP3A inhibitor is unavoidable, investigators should reduce the dose of abemaciclib according to the dose reduction table in Section 3.7.8.3. For participants receiving the original starting dose, the dose should be reduced to the first dose reduction level. For participants who have already had a dose reduction for tolerability, reduce the dose further to the second dose reduction level. For subjects receiving doses which do not have an appropriate dose reduction option, or who have already been dose reduced to the lowest possible dose level, the investigator may consider suspending abemaciclib for the duration of the strong CYP3A inhibitor medication. Dose suspensions ≥ 21 days must be discussed with Lilly CRP/CRS.

Upon discontinuation of the strong CYP3A inhibitor, the dose of abemaciclib may be re-escalated to the dose that was used before starting the strong inhibitor after a sufficient washout period (3 to 5 half-lives of the strong inhibitor). Re-escalation of abemaciclib dose requires review and approval from the Lilly CRP/CRS.

Inducers of CYP3A should be substituted or avoided if possible (see list below).

Coadministration with a CYP3A inducer ≥ 21 days must be discussed with the Lilly CRP/CRS.

Note: The information in this table is provided for guidance to investigators and does not preclude the use of these medications if clinically indicated. This list is intended to be exhaustive, but with available information continually evolving, the status of every relevant drug cannot be guaranteed. Please consult with the medical monitor in case of any doubt about a potential drug-drug interaction.

Strong Inducers of CYP3A	Special Status
Aminoglutethimide	Very limited use. Possibly available in Egypt and Lithuania
Apalutamide	
Carbamazepine (daily dose exceeding 600 mg)	
Enzalutamide	
Fosphenytoin (see also phenytoin)	
Ivosidenib	
Lumacaftor	
Mitotane	
Phenobarbital	
Phenytoin	
Rifabutin	
Rifampicin (rifampin)	
Rifapentine	
St John's wort	Supplement or food/drink
Moderate Inducers of CYP3A	
Bosentan	Supplement or food/drink
Carbamazepine (daily dose 600 mg or lower)	
Cenobamate	
Dabrafenib	
Danshen (Salvia miltiorrhiza)	
Efavirenz	
Elagolix	
Encorafenib	
Etravirine	
Genistein	
Lopinavir (alone)	
Lorlatinib	
Modafinil	
Nafcillin (intravenous)	Very limited use; Available in US
Pentobarbital	Very limited use
Primidone	Very limited use; available in US; importable into UK
Sotorasib	
Thioridazine	
Tocilizumab (atlizumab)	non-traditional mechanism: reverses the IL-6 mediated suppression of CYP3A activity in participants with rheumatoid arthritis
Strong Inhibitors of CYP3A	
Atazanavir and cobicistat	
Boceprevir	

Ceritinib	
Clarithromycin	
Cobicistat (see atazanavir and cobicistat)	
Conivaptan	
Danoprevir and ritonavir	
Elvitegravir and ritonavir	
Fosamprenavir and ritonavir	
Grapefruit juice	Supplement or food/drink
Idelalisib	
Indinavir and ritonavir	
Itraconazole	
Josamycin	Outside US
Ketoconazole	Very limited use
Lonafarnib	
Lopinavir and ritonavir	
Mifepristone	Very limited use; Cushing's disease in US
Nefazodone	Very limited use; Available in US
Nelfinavir	
Nirmatrelvir and ritonavir	
Posaconazole	
Ribociclib	
Ritonavir	
Saquinavir and ritonavir	
Telithromycin	
Tipranavir and ritonavir	
Tucatinib	
Viekirax (paritaprevir and ritonavir and ombitasvir and/or dasabuvir)	Outside of US
Voriconazole	

Guidance for Transporter Substrates

Abemaciclib inhibits the transporters P-glycoprotein, breast cancer resistance protein, organic cation transporter 2, multidrug and toxin extrusion protein 1 (MATE1), and MATE2-K. The observed serum creatinine increase in clinical studies with abemaciclib is likely due to inhibition of tubular secretion of creatinine via OCT2, MATE1, and MATE2-K. In vivo interactions of abemaciclib with narrow therapeutic index substrates of these transporters, such as digoxin and dabigatran may occur.

Irinotecan and Temozolomide

Refer to the product labels of irinotecan and temozolomide for information regarding concomitant medications.

Attachment 6. Protocol JP04 Addendum Abemaciclib Dosing Chart

BSA (m ²) for participants <18 years ^a	Abemaciclib dose (mg)
0.2	CCI
0.21-0.24	CCI
0.25-0.29	CCI
0.3-0.34	CCI
0.35-0.38	CCI
0.39-0.43	CCI
0.44-0.68	CCI
0.69-1.13	CCI
1.14-1.59	CCI
1.60+	CCI
All participants ≥18 years	CCI

^a BSA calculations are made using the Mosteller formula (Mosteller 1987)

Attachment 7. Protocol JP04 Addendum Contraceptive Guidance and Collection of Pregnancy Information

Definitions:

Woman of Childbearing Potential (WOCBP)

A woman is considered fertile following menarche and until becoming post-menopausal unless permanently sterile (see below).

If fertility is unclear (e.g. amenorrhea in adolescents or athletes) and a menstrual cycle cannot be confirmed before first dose of study intervention, additional evaluation should be considered.

Women in the following categories are not considered WOCBP:

1. Premenarchal
2. Female with 1 of the following:
 - Documented hysterectomy
 - Documented bilateral salpingectomy
 - Documented bilateral oophorectomy

For individuals with permanent infertility due to an alternate medical cause other than the above (e.g. Mullerian agenesis, androgen insensitivity), investigator discretion should be applied to determining study entry.

Note: Documentation can come from the site personnel's: review of the participant's medical records, medical examination, or medical history interview.

Fertile men

A man is considered fertile after puberty unless permanently sterile by bilateral orchidectomy.

Contraception Guidance:

CONTRACEPTIVES^a ALLOWED DURING THE STUDY INCLUDE:
Highly Effective Methods^b That Have Low User Dependency

 • Implantable progestogen-only hormone contraception associated with inhibition of ovulation^c • Intrauterine device • Intrauterine hormone-releasing system^c • Bilateral tubal occlusion • Vasectomized partner • (Vasectomized partner is a highly effective contraceptive method provided that the partner is the sole sexual partner of the woman of childbearing potential and the absence of sperm has been confirmed. If not, an additional highly effective method of contraception should be used. Spermatogenesis cycle is approximately 90 days.)
Highly Effective Methods^b That Are User Dependent

 • Combined (estrogen- and progestogen-containing) hormonal contraception associated with inhibition of ovulation^c 
 ○ oral ○ intravaginal ○ transdermal ○ injectable • Progestogen-only hormone contraception associated with inhibition of ovulation^c 
 ○ oral ○ injectable • Sexual abstinence (Sexual abstinence is considered a highly effective method only if defined as refraining from heterosexual intercourse during the entire period of risk associated with the study intervention. The reliability of sexual abstinence needs to be evaluated in relation to the duration of the study and the preferred and usual lifestyle of the participant.)

a) Contraceptive use by men or women should be consistent with local regulations regarding the use of contraceptive methods for those participating in clinical studies.
 
b) Failure rate of <1% per year when used consistently and correctly. Typical use failure rates differ from those when used consistently and correctly.
 
c) Male condoms must be used in addition to hormonal contraception. If locally required, in accordance with Clinical Trial Facilitation Group (CTFG) guidelines, acceptable contraceptive methods are limited to those which inhibit ovulation as the primary mode of action.
 
Note: Periodic abstinence (calendar, symptothermal, post-ovulation methods), withdrawal (coitus interruptus), spermicides only, and lactational amenorrhoea method (LAM) are not acceptable methods of contraception for this study. Male condom and female condom should not be used together (due to risk of failure with friction)

Collection of Pregnancy Information

Male participants with partners who become pregnant

- The investigator will attempt to collect pregnancy information on any male participant's female partner who becomes pregnant while the male participant is in this study. This applies only to male participants who receive abemaciclib.
- After obtaining the necessary signed informed consent from the pregnant female partner directly, the investigator will record pregnancy information on the appropriate form and submit it to the sponsor within 24 hours of learning of the partner's pregnancy. The female partner will also be followed to determine the outcome of the pregnancy. Information on the status of the mother and child will be forwarded to the sponsor. Generally, the follow-up will be no longer than 6 to 8 weeks following the estimated delivery date. Any termination of the pregnancy will be reported regardless of fetal status (presence or absence of anomalies) or indication for the procedure.

Female Participants who become pregnant

- The investigator will collect pregnancy information on any female participant who becomes pregnant while participating in this study. Information will be recorded on the appropriate form and submitted to the sponsor within 24 hours of learning of a participant's pregnancy.
- The participant will be followed to determine the outcome of the pregnancy. The investigator will collect follow-up information on the participant and the neonate and the information will be forwarded to the sponsor. Generally, follow-up will not be required for longer than 6 to 8 weeks beyond the estimated delivery date. Any termination of pregnancy will be reported, regardless of fetal status (presence or absence of anomalies) or indication for the procedure.
- While pregnancy itself is not considered to be an AE or SAE, any pregnancy complication or elective termination of a pregnancy will be reported as an AE or SAE. A spontaneous abortion is always considered to be an SAE and will be reported as such. Any post-study pregnancy related SAE considered reasonably related to the study intervention by the investigator will be reported to the sponsor as described in Section 9.2.1 of the CAMPFIRE Master Protocol. While the investigator is not obligated to actively seek this information in former study participants, he or she may learn of an SAE through spontaneous reporting.

Any female participant who becomes pregnant while participating in the study will discontinue study intervention and be withdrawn from the study.

Attachment 8. Protocol JP04 Addendum Provisions for Changes in Study Conduct During Exceptional Circumstances

Implementation of this appendix

The changes to procedures described in this appendix are temporary measures intended to be used only during specific time periods as directed by the sponsor in partnership with the investigator.

In Germany, the procedures outlined in this appendix are applicable only to the COVID-19 pandemic.

Exceptional circumstances

Exceptional circumstances are rare events that may cause disruptions to the conduct of the study. Examples include pandemics or natural disasters. These disruptions may limit the ability of the investigators, participants, or both to attend on-site visits or to conduct planned study procedures.

Implementing changes under exceptional circumstances

In an exceptional circumstance, after receiving the sponsor's written approval, sites may implement changes if permitted by local regulations.

After approval by local Ethical Review Boards, regulatory bodies and any other relevant local authorities, implementation of these exceptional circumstance changes will not typically require additional notification to these groups, unless they have specific requirements in which notification is required (for example, upon implementation and suspension of changes). All approvals and notifications must be retained in the study records.

If the sponsor grants written approval for changes in study conduct, the sponsor will also provide additional written guidance, if needed.

Considerations for making a change

The prevailing consideration for making a change is ensuring the safety of study participants. Additional important considerations for making a change are compliance with Good Clinical Practice, enabling participants to continue safely in the study and maintaining the integrity of the study.

Informed consent

Additional consent from the participant will be obtained, if required, for:

- participation in remote visits, as defined in Section "Remote Visits,"
- dispensation of additional study intervention during an extended treatment period,
- alternate delivery of study intervention and ancillary supplies, and

- provision of their personal or medical information required prior to implementation of these activities.

Changes in study conduct during exceptional circumstances

Changes in study conduct not described in this appendix, or not consistent with applicable local regulations, are not allowed.

The following changes in study conduct will not be considered protocol deviations.

Remote visits

Types of remote visits

Telemedicine:

Telephone or technology-assisted virtual visits, or both, are acceptable to complete appropriate assessments.

Mobile healthcare:

Healthcare visits may be performed by a mobile healthcare provider at locations other than the study site (for example, participant's home) when participants cannot travel to the site due to an exceptional circumstance if written approval is provided by the sponsor. Such visits will be performed by a mobile healthcare provider trained on the study.

Data capture

In source documents and the CRF, the study site should capture the visit method, with a specific explanation for any data missing because of missed in-person site visits.

Safety reporting

Regardless of the type of remote visits implemented, the protocol requirements regarding the reporting of adverse events (AEs), serious adverse events (SAEs), and product complaints remain unchanged.

Return to on-site visits

Every effort should be made to enable participants to return to on-site visits as soon as reasonably possible, while ensuring the safety of both the participants and the site staff.

Study intervention and ancillary supplies (including participant diaries)

When a participant is unable to go to the site to receive study supplies during normal on-site visits, the site should work with the sponsor to determine appropriate actions. These actions may include:

- asking the participant to go to the site and receive study supplies from site staff without completion of a full study visit,
- asking the participant's designee to go to the site and receive study supplies on a participant's behalf,

- arranging delivery of study supplies, and
- working with the sponsor to determine how study intervention that is typically administered on site will be administered to the participant; for example, during a mobile healthcare visit or at an alternate location such as an infusion center.

These requirements must be met before action is taken:

- Alternate delivery of study intervention should be performed in a manner that ensures product integrity. The existing protocol requirements for product accountability remain unchanged, including verification of participant's receipt of study supplies.
- When delivering supplies to a location other than the study site (for example, participant's home), the investigator, sponsor, or both should ensure oversight of the shipping process to ensure accountability and product quality (that is, storage conditions maintained and intact packaging upon receipt).
- Instructions may be provided to the participant or designee on the final disposition of any unused or completed study supplies.

If study intervention will be administered to the participant during a mobile healthcare visit or at an alternate location, this additional requirement must be met:

- Only authorized study personnel may supply, prepare or administer study intervention.

Documentation

Changes to study conduct will be documented

Sites will identify and document the details of how participants, visits types, and conducted activities were affected by exceptional circumstances. Dispensing/shipment records of study intervention and relevant communications, including delegation, should be filed with site study records.

Source documents at alternate locations

Source documents generated at a location other than the study site should be part of the investigator's source documentation and should be transferred to the site in a secure and timely manner.

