- [7] Women of reproductive potential must agree to use highly effective contraceptive precautions (and avoid sperm donation for males) during the trial. For abemaciclib, females should use contraception for at least 3 weeks following the last abemaciclib dose. After the last dose of irinotecan and temozolomide, females should use contraception for at least 6 months, and male participants with a WOCBP partner should use contraception for at least 3 months. Following last dose of temozolomide treatment, men must refrain from sperm donation per product label.

See [Attachment 7](#) for additional details on contraceptive guidance and the collection of pregnancy information.

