3.7. Treatments

3.7.1. Treatments Administered

Table JP04.6 shows the treatment regimens.

Table JP04.6. Treatment Regimens

Starting Doses Cycle = 21 days				
	Abemaciclib PO		Irinotecan IV (Days 1-5 each cycle)	Temozolomide PO (Days 1-5 each cycle)
	<18 years	≥18 years		
Arm A	55 mg/m ² BID (max dose 100 mg BID)	100 mg BID	50 mg/m ² /day × 5	100 mg/m ² /day × 5
Arm B	None		50 mg/m ² /day × 5	100 mg/m ² /day × 5
Authorized as defined by EU Clinical Trial Regulation	Authorized and not used according to EU authorization		Authorized and not used according to EU authorization	Authorized and not used according to EU authorization

Abbreviations: BID = twice daily; IV = intravenous; PO = orally.

Participants will begin dosing-assigned treatment on Cycle 1 Day 1. A cycle is defined as an interval of 21 days timed to irinotecan and temozolomide. The 21-day cycle, anchored to irinotecan and temozolomide, should be maintained throughout the treatment phase. Cycles may not be less than 21 days.

When delays are required, doses should be resumed at the earliest medically appropriate opportunity based on investigator judgment and dose adjustment guidelines (Section 3.7.8).

Treatment will continue until progression, unacceptable toxicity, or other discontinuation criteria are met (Section 3.8).

A delay to the start of a cycle of a dose due to holiday, weekend, weather, or other unforeseen circumstances will be permitted for a maximum of 7 days and not counted as a protocol deviation. In exceptional circumstances, a delay of >7 days is permitted upon agreement between the investigator and the Lilly CRP/CRS. Abemaciclib treatment may continue during the delay if there is sufficient drug supply and if there are no toxicities that would prevent treatment.

Irinotecan and temozolomide must be administered on 5 consecutive days.

Packaging and labeling

Treatments administered in the study will be supplied by the sponsor in accordance with current Good Manufacturing Practice. Study interventions will be labeled as appropriate for country requirements.

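### Partner pregnancies are collected only for men who receive abemaciclib, although the post-treatment contraception period for men is tied to irinotecan and temozolomide, which both arms receive

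*Protocol*

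**What the plan says.** Protocol Attachment 7, under the collection of pregnancy information for male participants, opens with a general rule: "The investigator will attempt to collect pregnancy information on any male participant's female partner who becomes pregnant while the male participant is in this study". The next sentence narrows it: "This applies only to male participants who receive abemaciclib". Where the rule applies, the partner is asked for consent, a form goes to the sponsor within 24 hours of the site learning of the pregnancy, the outcome is followed, and any termination is reported.

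Inclusion criterion 7 in Section 3.6.1.1 deals with reproductive precautions drug by drug:

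- Abemaciclib: "For abemaciclib, females should use contraception for at least 3 weeks following the last abemaciclib dose". No post-treatment period is given for men.
- Irinotecan and temozolomide: women are given a period of 6 months or more, counted from the final dose. The rule for men reads: "male participants with a WOCBP partner should use contraception for at least 3 months".
- Temozolomide: "Following last dose of temozolomide treatment, men must refrain from sperm donation per product label".

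Section 3.5.4 states that every randomized participant receives irinotecan plus temozolomide and that Arm A also receives abemaciclib. For female participants, Attachment 7 collects any pregnancy during participation, with no limit by arm or drug.

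**The concern.** The drug that triggers collection of partner pregnancies is the one for which criterion 7 states no post-treatment period for men. The two drugs for which it does state such a precaution do not trigger collection. An Arm B man is told to use contraception for at least 3 months after his chemotherapy because of a possible reproductive risk, yet if his partner conceives, the addendum gives the site no duty to collect or follow the pregnancy.

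What is at stake is safety information. Attachment 10 classes spontaneous abortion, fetal death and congenital anomaly as serious, so an adverse outcome here would matter individually even if it were the only one. Irinotecan and temozolomide are also study treatments, and Table JP04.6 lists each as "Authorized and not used according to EU authorization". That entry says nothing about reproductive risk. It does show that the two drugs are not being given simply as labelled care outside the study's remit.

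**Working it through.** The plan states no figure on this point, so the check is a comparison of the texts plus one piece of arithmetic.

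**Comparison by drug**

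| | Abemaciclib | Irinotecan and temozolomide |
|---|---|---|
| Given in (Section 3.5.4) | Arm A only | Arms A and B |
| Post-treatment contraception, women (criterion 7) | at least 3 weeks | at least 6 months |
| Post-treatment contraception, men (criterion 7) | none stated | at least 3 months |
| Post-dose limit on sperm donation (criterion 7) | none stated | yes, tied to temozolomide |
| Partner pregnancy collected (Attachment 7) | yes | not on the strength of these drugs alone |
| Participant's own pregnancy collected (Attachment 7) | yes | yes |

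The fifth row does not match the third and fourth. The sixth shows that the limit by drug applies only to partners of men.

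**Does another part of the documents restore collection?** Attachment 10 gives serious-event definitions that include abnormal pregnancy outcomes, but it defines an adverse event as an occurrence in a participant. It creates no duty to approach a participant's partner, obtain her consent or follow her pregnancy. The SAP's safety sections do not mention partner pregnancy. Nothing supplied restores collection for Arm B partners. Section 3.9.2 refers to the CAMPFIRE Master Protocol for adverse-event reporting, and that document could not be checked.

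**Number of men concerned**

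- Inputs: at least 45 participants, randomized 2:1 (Section 3.10.1).
- Arm B = 45 × 1/(2 + 1) = 15.
- The documents give neither the share of males nor the share with a partner of childbearing potential, so the affected group is anywhere from 0 to 15.
- If 40% to 65% are male (assumption), 15 × 0.40 = 6 and 15 × 0.65 = 9.75, or about 6 to 10 males. This is a ceiling for that assumption: eligibility starts at age 1 year, Attachment 7 counts males as fertile only after puberty, and not every man will have a partner of childbearing potential.

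**Expected events, for scale only.** Take 10 men for one year each (assumption) and the failure rate below 1% per year that Attachment 7 gives for its listed methods under consistent use. Then 10 × 1 × 0.01 = 0.1, so fewer than 0.1 partner pregnancies would be expected. Attachment 7 notes that typical use has different failure rates, so the true figure could be higher, but the count stays very small.

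**The case against.** The strongest reply is that this is a deliberate choice of scope. Criterion 7 sets contraception duties and Attachment 7 sets what data are collected, and the first does not logically dictate the second. A sponsor may limit active collection to its investigational agent, and Sections 3.3.2.3 and 3.3.2.4 describe the safety of irinotecan and temozolomide as well known. This has some force: the two texts can both be followed. It does not explain why pregnancies of female participants in Arm B are collected, since familiarity with the chemotherapy would apply equally to them, and the documents give no reason for the difference.

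The following objections stand and limit the point:

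- A reader might infer that all exposed pregnancies in Arm B go uncollected. They do not; only partner pregnancies are affected.
- A reader might infer that every Arm B partner event is certain to be missed. That cannot be established without the Master Protocol. The amendment history describes Attachment 7 as adding to what the Master Protocol contains.
- A reader might infer a biased comparison between arms, with Arm A outcomes wrongly attributed to abemaciclib for lack of a comparator. With so few events expected, and no pregnancy comparison among the SAP's safety summaries, this is not a realistic harm.
- A reader might infer that the protocol sees no male risk from abemaciclib. Criterion 7 also has males avoid sperm donation throughout the trial without naming a drug, so the missing post-dose period does not show that.
- A treated woman's own pregnancy and a pregnancy in a treated man's partner are different exposures. The contrast between the sexes shows an unexplained difference in handling, not unequal treatment of an identical risk.

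**Conclusion.** The point holds in a limited form. Under the addendum as written, partner pregnancies of Arm B men are not collected or followed to outcome, although the protocol's only post-treatment precautions for men are tied to drugs those men receive. The same applies to an Arm A man who never starts abemaciclib, a marginal case.

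The group is a subset of about 15 participants at the minimum sample size, and few or no events are expected. The conclusion rests on the addendum and SAP alone and assumes that the Master Protocol has no rule that overrides the restriction. The consequence is a small gap in safety follow-up. Sample size, error rates, the primary endpoint and the comparison of the arms are untouched. It merits correction because the rule is explicit and sites will follow it, and because the remedy is one sentence.

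**What to change.** Reconcile Attachment 7 with criterion 7. The simplest way is to delete the restricting sentence, which leaves the preceding rule covering the partner of any male participant. The alternative is to reword it so that it covers male participants who receive any study treatment.

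Keep the existing window, which runs for as long as the man is in the study. Long-term follow-up lasts until death, withdrawal or study completion, so ending collection at the close of a contraception period could shorten the window for men still in follow-up. Such an end date would also be undefined for abemaciclib, for which criterion 7 gives men no period. If the sponsor wants coverage of the post-treatment contraception period for men who leave the study early, it should be added to the current window, not substituted for it.

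If the restriction is intended, the protocol should give the reason and say whether the Master Protocol covers Arm B partners.

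The cost is one sentence in an amendment, with matching edits to the eCRF instructions and the partner consent form. The pregnancy form and consent process already exist; the burden is their use in very few extra cases. The change concerns data collection only and alters no contraception or treatment rule.
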